### **Analytical Plan**

For the primary analysis, logistic regression of success criterion (anti-Xa activity level < 0.2 IU/mL) and 95% confidence limits at a success level (<0.2) of 95% likelihood will be utilized. For secondary analyses we plan to describe the best-fit function for anti-Xa activity levels over time. We also plan to explore clinical predictors for any anti-Xa activity levels > 1 standard deviation over the mean from the above function.

Protocol version:

Template updated 9.24.14

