Historical data from a previous publication (which showed that at 24-hours 58% of patients had an anti-Xa level  $\geq 0.21\text{IU}/\text{mL}$ ) was used to conduct a power analysis. In this prior study, data points were collected between 23.25-hours and 32-hours, and anti-Xa levels ranged between 0 and  $0.54\text{IU}/\text{mL}$ . Assuming a similar relationship between anti-Xa activity levels and time observed in the original study pertains to later times, simulations using a sample size of 150 patients resulted in a threshold of approximately 29-hours with 95% confidence limits of approximately 28-hours and 33-hours. It was felt that a 5-hour window of the 95% confidence limit would provide acceptable guidance for clinical care. We expect some drop out and patient loss since some patients may have their surgical procedure cancelled following enrollment/randomization. In addition, occasionally the decision regarding the use of bridging therapy changes following a patient's visit to the preoperative assessment clinic. Therefore, we plan to enroll upwards of 180 patients until 150 patients have completed the study and have their data available for analysis.

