### **Interventions and Interactions**

- Patients on treatment dose enoxaparin will be identified at the time of their preoperative anesthesia consultation. These patients will be seen in the preoperative assessment clinic by a study team member and the study will be discussed with them at that time.
- Patients may elect to consent during their preoperative anesthesia consultation visit, or if they would like to think it over and talk with family/friends, a study team member will follow-up with them by phone to answer further questions.
- After consenting to the study, patients will be randomized to one of two groups.
  - Group one will be instructed to administer their last dose of enoxaparin at 07:00 in the morning on the day prior to their scheduled surgery date. This will mean

Protocol version:

Template updated 9.24.14

that patients who have their surgery scheduled for 07:00 the following day will be 24-hours removed from their last dose. Patients presenting for surgery later in the day would be slightly farther removed from their last dose, however this is currently considered normal clinical practice.

- Group 2 will be instructed to administer their last dose of enoxaparin at 19:00 in the evening two days prior to their scheduled surgery date. Patients presenting for surgery at 07:00 two days later will be 36-hours removed from their last dose. Patients presenting for surgery later in the day would be slightly farther removed from their last dose, but again this mimics normal clinical practice in which the timing of the last dose of self-administered enoxaparin is not routinely adjusted based on the scheduled surgical start time.
- All patients consented for the study will be called by a study team member or study coordinator two days before their surgical date to ensure they understand when they are supposed to self-administer their last dose of enoxaparin.
- Upon arrival for surgery, all consented patients will have demographic information recorded (age, weight, gender) as well as the enoxaparin dosage and the timing of their last administration.
- All patients in the study will have a blood sample drawn. Two laboratory tests will be sent.
  - 1). Anti-Xa level assay (Heparin Assay)
  - 2). Basic Metabolic Panel (BMP) (for evaluation of creatinine).
- When feasible, blood sampling will be performed at the same time that intravenous access for fluid/medication administration is obtained to minimize patient discomfort.

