### **Outcome Measure(s)**

The primary outcome of the study is the measurement of anti-Xa activity levels following the last treatment dose of enoxaparin in patients presenting for elective surgery. Anti-Xa level activity will be measured using a chromogenic assay and a hybrid curve calibrated to both heparin and enoxaparin. The randomization of patients to either the 24-hour group or the 36-hour group will allow for modeling, which will generate a prediction of the time point at which the level of anti-Xa activity can reliably be assumed to be lower than 0.2IU/mL.

Secondary outcomes will include determining the relationship of anti-Xa level activity over time (by using curve fitting or best-fit function) as well as attempting to determine if there are any patient conditions or characteristics that can predict delayed clearance of enoxaparin (elevated anti-Xa levels).

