## **Appendix**

1. Data collection form
2. Consent form

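### The search for predictors of delayed clearance rests on an undefined cut at 1 SD above the fitted curve; a censored regression of the continuous anti-Xa level would use the same data better.

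*Combined protocol and SAP*

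**What the plan says.** The protocol's Outcome Measure(s) section sets a secondary aim of determining whether there are "any patient conditions or characteristics that can predict delayed clearance of enoxaparin (elevated anti-Xa levels"). The Analytical Plan gives that aim one sentence: the investigators will "explore clinical predictors for any anti-Xa activity levels > 1 standard deviation over the mean from the above function". The function meant is the best-fit curve of anti-Xa level over time.

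The mean is therefore tied to the curve, but the SD is not defined: raw or log scale, pooled or time-specific, residual or overall. No test is named, and no section plans a regression of the level on patient characteristics.

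The data for such a regression are already collected. Every patient has an anti-Xa level. Interventions and Interactions has "demographic information recorded (age, weight, gender) as well as the enoxaparin dosage and the timing of their last administration", and a "Basic Metabolic Panel (BMP) (for evaluation of creatinine"). The Appendix also lists a "Data collection form", which may hold further candidates.

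On the spread of levels, Sample Size (under Subjects selection criteria) says of the earlier study that "data points were collected between 23.25-hours and 32-hours, and anti-Xa levels ranged between 0 and" 0.54 IU/mL. Levels thus reached the bottom of the scale even before 36 hours.

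**The concern.** If the sentence is carried out as written, the likely analysis turns each level into high or not high and compares characteristics between the two. That discards how far above or below the curve each patient lies, so a real predictor is easier to miss. The undefined SD also leaves open who counts as a slow clearer, and that choice could be made after the data are seen. What is at stake is the sensitivity and reproducibility of one exploratory secondary analysis, not the primary threshold.

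**Working it through.** **Inputs from the protocol.** 150 evaluable patients, taken as 75 per group. Groups timed at 24 and 36 h for a 07:00 start, later for later starts. From Sample Size: an earlier study "which showed that at 24-hours 58% of patients had an anti-Xa level" of at least 0.21 IU/mL, and "simulations using a sample size of 150 patients resulted in a threshold of approximately 29-hours". I read that threshold with the Analytical Plan's 95% criterion, so 95% of levels are below 0.2 IU/mL at 29 h.

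**Assumed, not in the protocol.** Log-normal scatter about an exponential decline; log SD s = 0.3, 0.42 or 0.6; assay limit 0.05 or 0.10 IU/mL; sampling spread over 4 or 8 h per group; a predictor present in 30% of patients that raises levels by 25% or 40%.

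**The plan's own figure.** None is given for this analysis. The primary figure is about 29 h (95% limits about 28 to 33 h). A logistic curve through 42% success at 24 h and 95% at 29 h, sampled at 24–32 and 36–44 h with n = 150, gives Fieller limits of about 27.5 to 33.6 h. The stated figure is plausible, but its simulation inputs are not given. It serves here only as an anchor.

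**Step 1. Loss from the cut, no censoring.** For normal residuals with constant SD, a cut at +1 SD keeps φ(1)²/{Φ(1)[1−Φ(1)]} = 0.2420²/(0.8413 × 0.1587) = 0.439. It flags 150 × 0.1587 = 23.8 patients and carries the information of 150 × 0.439 ≈ 66. If only 8% are flagged (cut at 1.405 SD), the share kept is 0.300.

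**Step 2. Curve through the anchors.** Median at 24 h = 0.21·exp(0.202s); median at 29 h = 0.2·exp(−1.645s). For s = 0.42 these are 0.229 and 0.100, so the decay rate is ln(0.229/0.100)/5 ≈ 0.165 per hour, the half-life 0.693/0.165 = 4.2 h, and the 36-h median 0.032. Over s = 0.3 to 0.6, the half-life is 5.7 to 3.0 h and the 36-h median 0.053 to 0.015.

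**Step 3. Information with an assay limit.** Let c = [ln(limit) − ln(median at t)]/s. A censored regression keeps 1 − Φ(c) + cφ(c) + φ(c)²/Φ(c) per patient; summed over 150, that equals 54–120 fully measured patients. For a flag at mean(t) plus a pooled raw residual SD, let u be the cut on the same standardised log scale and p the share flagged. The information is [mean φ(u)]²/[p(1−p)] = 0.173–0.246, or 26–37 patients. The ratio is 31–51% (35–57% if the flag analysis adjusts for time). Example: s = 0.42, 8-h spread, limit 0.05 gives 31 against 81.

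**Step 4. How many are flagged.** Expected number = 150 × the mean over t of 1 − Φ{[ln max(cut, limit) − ln median(t)]/s}, since a value below the limit cannot be seen as high. Pooled raw, time-specific raw and log residual SDs give about 9–23 of 150 across scenarios: 11–23 at s = 0.3, and about 9–15 at s = 0.42–0.6.

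**Step 5. Power.** Chi-square on each flag against a likelihood-ratio test in the censored regression, 8-h spread.

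| Assumption | Result |
|---|---|
| Log-normal decline, 12 settings, 800 trials each, regression size-adjusted | Regression 24–100%, pooled raw flag 14–91%, log flag 18–97%. Regression higher in all 12, by 9–35 points over pooled raw and 3–28 over log |
| Half-life 7 or 12 h, 8 settings | Regression 66–99%, flags 28–90%; regression higher in all 8 |
| Effect on the upper tail only, 12 settings | Regression above pooled raw in all 12 (3–23 points); against log, higher in 8, tied in 3, lower in 1 (53% v 60%) |
| Constant raw scatter (SD 0.05), 4 settings | Log-scale regression below pooled raw flag in 2 (31% v 34%, 65% v 74%); raw-scale censored regression above it in all 4 (69–99% v 34–72%) |

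The half-life and tail rows, and the log-scale regression in the last row, used 600 trials each and no size adjustment; the raw-scale runs used 300. Unadjusted null rejection was 4.9–6.2% for the regression and 3.6–5.7% for the flags. In a smaller separate run of the 12 log-normal settings (150 trials each), the log flag was allowed to see exact values below the limit. The regression was then higher in 6, tied in 1 and lower in 5 against the log flag, but still above the pooled raw flag in all 12.

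**The case against.** **The yes/no test is inferred.** The plan says only that predictors will be explored, and a descriptive look at high levels would fit its words. This stands: the efficiency and power figures apply only if the cut is used as an outcome. But an aim of finding what predicts delayed clearance needs some comparison, and even a description needs a defined SD.

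**A reader might infer that the choice of SD alone moves the number flagged from about 5 to 24 of 150.** The documents do not support that. The low end (5–9) needs the SD of all levels, including the fall between 24 and 36 h, paired with a mean taken from the curve; scatter about the curve is the more natural reading. The high end (24, log SD) treats every level as measurable. Step 4 shows the narrower range once the assay limit is applied. The readings differ more if scatter is small or the half-life longer.

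**A reader might also infer that a pooled raw-scale SD is what draws the flags from the 24-hour arm.** That is largely the assay floor. On the anchors, 72–100% of 36-hour levels fall below 0.05, and at s = 0.42–0.6 a log flag with the limit applied also takes only 0–3 patients from that arm. No choice of analysis restores that information.

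**The simulations favour the regression.** The main runs generate data from the model that is then fitted, margins near 3 points are within simulation error, and the power ranges mostly reflect assumed effect sizes, scatter and limits. This stands, and it limits the claim against a log flag. The advantage over a pooled raw flag is firmer, provided the regression is fitted on the scale where scatter is constant.

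**The target may be the high tail.** Delayed clearance can reasonably mean unusually high levels, and a mean-shift model answers a related but not identical question. That is a reason to keep a defined flag alongside the regression, not to rely on it alone.

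**Conclusion.** The concern holds as a minor one. The only stated method for the delayed-clearance aim is a cut with an undefined SD and no named test. Used as a yes/no outcome it keeps about 44% of the available information in the ideal normal case. Against the fairer benchmark of a regression that is itself censored, a pooled raw flag keeps about 31–51%. Both figures rest on assumptions: the first on normal residuals with constant SD, the second on the decay form, scatter and assay limit set out above. The margin over a log-scale flag depends on censoring and on the form of the effect, and a pure upper-tail effect can favour that flag slightly. The undefined SD and the absence of a continuous predictor model need no assumption. The analysis is exploratory, and the primary logistic regression and the sample size of 150 are unaffected.

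**What to change.** Reword the last sentence of the Analytical Plan so that:

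- The main predictor analysis is a regression of the continuous anti-Xa level, left-censored at the assay limit, on hours since last dose plus the collected candidates: enoxaparin dosage, age, weight, gender, creatinine, and any others on the data collection form.
- The log scale is the default. Residual spread is checked against time first, and the raw scale is used if spread is constant there.
- Each effect is reported with a 95% CI (as a ratio of levels on the log scale), with the assay limit and the number of patients below it per arm.
- The flag at more than 1 SD is kept as description only, with the SD defined as that of time-standardised residuals on the modelling scale.

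The cost is wording: same data, no added patients or procedures. There are downsides. The model adds a scale and a censoring assumption, and the documents do not give the assay limit, so it must be obtained and stated. The 36-hour arm may add little: its 75 patients count as 0–45 fully measured ones on the anchors, or 7–75 if the half-life is 7–12 h. A mean-shift model can be slightly less sensitive to an effect confined to the upper tail.

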## **Human Subjects Protection**

### **Subject Recruitment Methods**

Patients on treatment dose enoxaparin will be identified at the time of their preoperative anesthesia consultation. These patients will be seen in the preoperative assessment clinic by a study team member and the study will be discussed with them. They will be given information related to the study (consent form). Patients may elect to consent to participation that day, or a study team member will follow-up with them by phone two days before their surgery to answer questions. If they choose to participate at that time the consent paperwork will be completed the day of surgery, but they will be randomized and instructed on when to self-administer their last treatment dose of enoxaparin prior to surgery.

### **Informed Consent**

Signed informed consent will be obtained from each subject. Only providers listed as a primary or co-investigator, study team member or study coordinator will obtain written informed consent.

### **Confidentiality and Privacy**

Confidentiality will be protected by collecting only information needed to assess study outcomes, minimizing to the fullest extent possible the collection of any information that could directly identify subjects, and maintaining all study information in a secure manner. To help ensure subject privacy and confidentiality, only a unique study identifier will appear on the data collection form. Any collected patient identifying information corresponding to the unique study identifier will be maintained on a linkage file, stored separately from the data. The linkage file will be kept secure, with access limited to designated study personnel. Following data collection subject identifying information will be destroyed 3 years after closure of the study by shredding the documentation, consistent with data validation and study design, producing an anonymous analytical data set. Data access will be limited to study staff. Data and records will be kept locked and secured, with any computer data password protected. No reference to any individual participant will appear in reports, presentations, or publications that may arise from the study.

### **Data and Safety Monitoring**

The principal investigator will be responsible for the overall monitoring of the data and safety of study participants. The principal investigator will be assisted by other members of the study staff.

The cost of both laboratory tests (anti-Xa level and BMP) will not be billed to the patient. These costs will be covered by the study sponsor (Department of Anesthesiology).

### **Reporting of Unanticipated Problems, Adverse Events or Deviations**

Any unanticipated problems, serious and unexpected adverse events, deviations or protocol changes will be promptly reported by the principal investigator or designated member of the research team to the IRB and sponsor or appropriate government agency if appropriate.

## **Appendix**

1. Data collection form
2. Consent form
